- A) The only study with a genetically similar population accepting the likelihood that in a predominantly Northern American cohort with high treatment rates a disproportionate number of high risk aneurysms (for example with dome irregularity and blebs) were treated before entry to the study.
- B) The only study with no selection or follow up bias accepting that this study found a markedly higher rate of rupture (26% vs 0% in ISUIA over 30 years) for the most common types of aneurysm (Juvela 2013), but that this difference may also be due to genetic or environmental differences in the Finnish population.
- C) The largest available study accepting the inherent biases introduced by combining studies of different and non-overlapping populations all with markedly different risk profiles.

There is therefore a pressing need for more research into the natural history of unruptured aneurysms. Specifically, the PHASES score, whilst used by 24 out of 30 neurosurgery units in the UK (unpublished data), has never been validated for use in a UK population. **Aim 1 - To validate the PHASES score in a UK population.**

The PHASES model only used 6 available patient and aneurysm characteristics for prediction. There are many more that are believed to have a large influence on risk but have not been considered. Examples include aspirin use, statin use, smoking, aneurysm irregularity, multiple aneurysms, family history of aneurysms/SAH and polycystic kidney disease. Therefore:

Aim 2 - To develop a new prediction model including all described predictors of risk.

Most clinicians believe that rupture risk is higher early after aneurysm formation and reduces with time. However, practically all clinical decisions are made by projecting estimates of short-term risk over a patient's lifetime (assuming a constant risk). For example, 68% of patients in PHASES came from a study with just 1.0 year of follow up which is reported as a 5 year risk in PHASES which is then extrapolated by clinicians to 30 year/lifetime risks. Therefore, very small errors in 1 year rates can lead to very large errors in lifetime risks. Moreover, none of the studies accounted for whether the aneurysm was a new diagnosis at time of recruitment or not. Data is therefore needed to determine the long-term risks of UIAs and assess if the early and late risks are the same. Therefore: **Aim 3 - To report long-term risk of aneurysm rupture.**

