subarachnoid haemorrhage other or unspecified and they subsequently died within 30 days (based on the very low rate of mortality from non-aneurysmal SAH) and did not have any additional codes for trauma indicating a non-aneurysmal event.

Data collection - other considerations - central HES ONS data

Last follow-up for each patient will be set as the time at which the HES search was performed, or the patient was unregistered with a GP in the UK or date of death, or the aneurysm was treated, whichever is earliest.

Additionally, we will record

- 1. race
- 2. I10 essential (primary) hypertension
- 3. Z72.0 tobacco use
- 4. F17.2 tobacco dependence

And use these to complete any missing baseline data. Where baseline data and HES conflict, the baseline data will be used. Where neither is available, after assessment for any bias (missing completely at random MCAR, missing at random MAR, missing not at random MNAR) multiple imputation will be used.

Statistical analysis - Aim 1 - PHASES validation

The PHASES study provides the coefficients from their Cox regression model and baseline survival at 5 years that allows the absolute 5-year risk of rupture, to be calculated for all patients who are not censored before 5 years, using age, whether the patients has hypertension, history of SAH, size of aneurysm (3 categories) and location of aneurysm. The time to censoring will be calculated (death or date of HES search or date unregistered from GP practice whichever is first) to ensure 5 years of follow up if rupture has not occurred. Discrimination will be assessed using Harrell's C-index of concordance and Royston and Sauerbrei's D statistic. Calibration will be assessed at the 5 year time point using the method in Royston (2014). These will be used to calculate the number of SAH events per 5 years for each PHASES score (0 to 12+) and expressed as a percentage with 95% confidence interval to compare to the PHASES estimates.

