A new risk prediction model for rupture will be developed using the total data set, including the additional possible risk factors. The Cox regression model will be used for risk of rupture. The absolute risks can be estimated at relevant time intervals, 2, 5 and 10 years. Numbers of missing values will be summarised for each factor. Multiple imputation will be used to replace missing values. Discrimination of the final model will be assessed with the Harrell's c-statistic. Internal validity will be assessed by bootstrap resampling.

Additionally, the following sensitivity analyses will be performed:

In view that a significant number of aneurysms are anticipated to have grown and subsequently treated on follow up, any cases noted to have undergone treatment for aneurysm growth will be included in a model predicting the risk of rupture or treatment for aneurysm growth. In view that it is anticipated that a number of unexplained deaths will be captured where it will not be possible to resolve if the cause was SAH or not, a model predicting aneurysm rupture or unexplained or unattended death (R 96 and 98) will be built.

Statistical analysis - Aim 3 - Long term rupture rates

It is anticipated that initially follow up times will range from months to 15 years. This will be insufficient to definitively answer what the long term risks posed by aneurysms are. However, a model will be built including a term for new diagnosis vs known diagnosis. This will establish if rupture rates are similar between patients with new and prior diagnoses.

All patients, including those who underwent aneurysm occlusion, will be included in time-to-event analysis which will cover the whole duration of available follow-up. This will include Kaplan-Meier and proportional hazards models for univariate and multivariate survival curve fitting. A cumulative Hazard plot will be used to assess if rupture risk is constant or varies with time from diagnosis.

Longer term, HES searches will be repeated periodically using unique HES identifiers generated by DARS at the first HES search. These searches will identify any late events of SAH due to aneurysm rupture and models will be built to predict true long-term risk.

Data management

Patient confidentiality

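### Aim 3 assesses whether rupture risk is constant from a cumulative hazard plot with no adjustment attached; selective treatment can bend that plot downward even if every aneurysm's own risk is constant

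*Protocol*

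**What the plan says.** Section 1 sets the question. "Most clinicians believe that rupture risk is higher early after aneurysm formation and reduces with time", whereas practical decisions project short-term risk over a lifetime as if it were constant. Aim 3, a primary aim, is to report long-term risk, and Section 1 asks whether early and late risks are the same.

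The analysis is in Section 5, Aim 3:

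- On who is analysed: "All patients, including those who underwent aneurysm occlusion, will be included in time-to-event analysis which will cover the whole duration of available follow-up".
- On the models: "This will include Kaplan-Meier and proportional hazards models for univariate and multivariate survival curve fitting".
- On constancy: "A cumulative Hazard plot will be used to assess if rupture risk is constant or varies with time from diagnosis".
- On earlier diagnosis: "a model will be built including a term for new diagnosis vs known diagnosis".

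Section 5 (data collection, other considerations) defines last follow-up as the earliest of several dates, ending with "or date of death, or the aneurysm was treated, whichever is earliest".

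On treatment in this cohort, Section 5, Aim 2 says that "a significant number of aneurysms are anticipated to have grown and subsequently treated on follow up". Section 1 criticises the earlier international cohort because selection for treatment was not random and because 32% of those first managed conservatively were later treated. It also accepts as likely that high-risk aneurysms were disproportionately treated before entering that cohort.

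**The concern.** The question in Section 1 concerns an aneurysm's own risk over time. An unadjusted cumulative hazard plot answers a different one: is the average hazard of whoever remains at risk flat? That average moves with case mix. If higher-risk aneurysms are treated preferentially and leave follow-up, those remaining are increasingly low-risk and the curve flattens with no change in any individual risk.

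The protocol supplies the preconditions: heterogeneous risk (five-year rates of 0% below 7 mm and 2.6% at 7-12 mm), selective treatment, and follow-up that ends at treatment. The artefact also points the same way as the belief being examined. A reader could take a flattening curve as evidence that risk declines and discount the lifetime risk of patients whose risk has not fallen.

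This is separate from whether the overall level of risk is underestimated. It concerns a spurious time trend in the tool named for judging constancy.

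**Working it through.** **The plan's own rate.** Section 7.2.1 uses 51 ruptures in 1,692 patients over 4.1 years: 51 / (1,692 × 4.1) = 51 / 6,937.2 = 0.735% per year. Sixty events then need 60 / 0.0073517 = 8,161 years, as stated. The protocol gives no figure for the plot itself. Everything below holds each aneurysm's hazard constant; the risk mix, treatment shares and timing are assumptions.

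**Step 1. Selective treatment in year 1.** Take 30% of aneurysms at 1.75%/yr and 70% at 0.307%/yr. The starting mean is 0.3 × 1.75 + 0.7 × 0.307 = 0.740%/yr. Ignoring rupture and death, the mean among those left is:

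- 60% of high-risk and 10% of low-risk treated: (0.12 × 1.75 + 0.63 × 0.307) / 0.75 = 0.538, a fall of 27%.
- 40% and 20% treated: (0.18 × 1.75 + 0.56 × 0.307) / 0.74 = 0.658, a fall of 11%.
- Equal shares treated: 0.740, no fall.

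**Step 2. Treatment spread over time (mean 1 year), with depletion by rupture.** Let w be the group share, λ its constant hazard and p the proportion treated. Then

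S(t) = exp(−λt) × [(1 − p) + p × exp(−t)], and pooled h(t) = Σ wλS(t) / Σ wS(t).

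Assume 25% high-risk and a starting mean of 0.735%/yr. For a hazard ratio of 5, the low-risk hazard is 0.735 / (0.75 + 0.25 × 5) = 0.368 and the high-risk hazard 1.838%/yr. With 20% of low-risk and 60% of high-risk treated (30% overall), S(10) = 0.964 × 0.800 = 0.771 for low-risk and 0.832 × 0.400 = 0.333 for high-risk. So

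h(10) = (0.75 × 0.368 × 0.771 + 0.25 × 1.838 × 0.333) / (0.75 × 0.771 + 0.25 × 0.333) = 0.366 / 0.662 = 0.553%/yr.

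| Hazard ratio | Treated, low / high | Year 0 | 1 | 5 | 10 | Fall by year 10 |
|---|---|---|---|---|---|---|
| 3 | 20% / 60% | 0.735 | 0.676 | 0.625 | 0.619 | 16% |
| 5 | 20% / 60% | 0.735 | 0.646 | 0.566 | 0.553 | 25% |
| 10 | 20% / 60% | 0.735 | 0.610 | 0.495 | 0.470 | 36% |
| 5 | 60% / 95% | 0.735 | 0.624 | 0.429 | 0.419 | 43% |

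The last row treats 69% overall, close to the 72% that Section 1 reports for the earlier cohort. A more extreme split (ratio 10, 10% / 80%) reaches 0.342, a fall of 53%.

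**Step 3. Controls.** With equal risk and censoring at treatment, h stays at 0.735 throughout. With heterogeneous risk but treatment unrelated to it (32% in both groups), the value at year 10 is the same as with no treatment at all: 0.661 at ratio 10. That 10% is depletion by rupture alone. Treatment adds to the bend only when it is selective.

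**Step 4. If treated patients stay in the risk set.** Assume no rupture after treatment. With 20% / 60% treated, the ratio 5 scenario falls to 0.381 at year 10. Even with equal risk the curve falls from 0.735 to 0.504. Baseline adjustment would not remove this.

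**Step 5. Does conditioning on risk help?** In simulations of the four tabulated scenarios (22,781 patients, 0.5 to 15 years of administrative follow-up, 2%/yr death), the rate after two years was compared with the rate in the first two, one-sided at 2.5%. A false fall was declared in 17%, 49%, 77% and 96% of runs unadjusted, and in 2% to 4% when stratified by true risk group.

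Real predictors are imperfect. In a separate simulation with the Step 1 hazards and 60% / 10% treated in year 1, then 3%/yr in both groups, a five-band test at 5% rejected constancy in 28% of runs unadjusted. It still rejected in 18% after adjustment with 20% of patients misclassified.

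**The case against.** Several points on the other side stand.

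- The protocol does not say the plot is single or pooled. That is a reading of the all-patients sentence and of the absence of any stratification. A SAP could stratify the plot or derive it from the multivariable models named just before it.
- The protocol plans a plot, with no significance test or decision rule. The rejection rates in Step 5 belong to an added test and are not error rates of the plan. They also move with later treatment: the 28% becomes 58% if treatment after year 1 runs at 10% v 3%/yr in high- and low-risk aneurysms.
- A reader might infer that high-risk aneurysms are treated mostly soon after diagnosis. No section gives treatment timing, and Section 8.4 says most patients are advised against treatment.
- A reader might also infer that Aim 3 would confirm falling risk whatever the truth. The documents do not support that. The bend can be modest, and no scenario with truly rising risk was examined.
- The plan also has the new-versus-known term, concedes that present follow-up cannot settle long-term risk, and foresees repeat searches.

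These points limit the claim but do not remove it. The protocol names the tool for judging constancy and gives it no protection against selection. The new-versus-known term compares patient groups, proportional hazards coefficients do not describe the shape of the baseline hazard, and longer follow-up does not undo selective treatment.

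**Conclusion.** The point holds as a weakness in a stated choice of method. An unadjusted cumulative hazard plot cannot separate a true fall in an aneurysm's risk from a change in who remains under observation. The direction needs only heterogeneous risk and treatment that favours higher-risk aneurysms, both of which the protocol describes.

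The size is not fixed by the documents. Across the main assumed scenarios it is roughly 10% to 43% (11% for the milder year-1 split, 43% for heavy treatment), and more extreme selection gives more. If treatment is unrelated to risk it contributes nothing, and only the smaller depletion by rupture remains.

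Section 5 also needs reconciling with itself on treated patients. Including them up to treatment is compatible with the last-follow-up rule; keeping them for the whole available follow-up is not. The curve falls under either reading when treatment is selective, and falls further if they stay in. Conditioning on measured risk factors is a clear improvement but only a partial remedy.

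**What to change.** In Section 5, Aim 3:

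1. Base the constancy conclusion on rupture rates by band of time since diagnosis (for example 0-1, 1-2, 2-5, 5-10 and over 10 years). Take them from a piecewise-exponential/Poisson or flexible parametric model that includes the PHASES items and the Aim 2 predictors, and assess the time bands within that model.
2. Show cumulative hazard plots by size and site stratum.
3. Keep the unadjusted plot as description only, and say that its shape also reflects selective treatment.
4. Reconcile the last-follow-up definition with the Aim 3 sentence on patients who had occlusion, so that one statement says what person-time treated patients contribute.
5. Attach a caveat that selection on growth, or on features not recorded at baseline, is reduced only in part. Growth is not a baseline item, and a bleb not mentioned in the radiology report is recorded as absent.

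The cost is a few lines of text and one extra model on covariates already collected. The price is wider intervals in the late bands.

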6 STUDY SETTING

The study will be conducted at up to 30 neurosurgery units in the UK. Patient identification and baseline clinical data will be collected from their locally held medical notes and stored on their own NHS servers. Access to patient medical records by the local direct clinical care team will be either electronic or manual depending the document storage method of the individual unit. The identification and baseline data collection by the direct clinical care team, in each neurosurgery unit maximises patient confidentiality and minimises the number of people who have access to identifiable medical records.

The coordinating unit (University Hospitals Southampton NHS FT) will be the site at which patient information is uploaded to HES/PEDW/SMR. It will also be the site where pseudonymised data is analysed. There are no site specific requirements dictating these be done in Southampton however this site has been chosen for analysis as it is the base where [name] and [name] currently work as clinicians. Pseudonymised data may also be analysed by [name] at the University of Oxford although she will have access to the pseudonymised list only. Similarly, pseudonymised data may also be analysed by contributors at participating centres.

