3 THEORETICAL FRAMEWORK

The study is designed as a UK based multi-centre study which incorporates retrospective patient identification combined with outcomes recorded in a prospective database.

NHS Health Research Authority

The first stage of the study is for individual neurosurgery units to identify their patients with an unruptured aneurysm and collect baseline data about that aneurysm. Most patients with unruptured aneurysms are managed as outpatients and assessed in a neurosciences unit in the UK. This should identify a large cohort of patients and the necessary aneurysm variables to predict risk are best recorded in local medical notes.

Searches will be done retrospectively over a period of up to 2006-2020. Patients can be identified from sources such as clinic letters, MDT discussions or radiology reports. A retrospective design allows the identification of patients diagnosed up to 15 years ago and thus the length of follow-up achievable will exceed the 5 years currently used in PHASES. Given that UIA can rupture at any point in a patient's lifetime the longer the follow-up achieved will make the results more translatable to the actual patient. Trying to achieve the same length of follow-up with a prospective study would take considerably more time and financial investment.

This study is best done as a multi-centre design because of the large number of patients required. UIA rupture is uncommon (approximately 1% per year) and thus to reach the minimum number of ruptures required to test the current PHASES model a much larger overall cohort of UIA will be required. This is only realistically achievable by many neurosurgical units pooling their patient numbers.

The second stage in this study is to compile the patients into a single cohort and link them to national databases for hospital admissions (HES/PEDW/SMR) for the UK. Every hospital admission in the country is recorded on one of these databases with the corresponding codes for diagnosis during that admission. Searching the cohort against these databases will return all admissions following diagnosis of a ruptured aneurysm.

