- Population: European/North American, Finnish, Japanese (where race cannot be confirmed it will be assumed to be non-Finnish and non-Japanese on the basis that there is a low incidence of these populations in the UK and their presence would usually be considered noteworthy in a clinical note.

The additional desirable covariates at time of diagnosis will include:

- aspirin use any dose used >3* per week
- statin use any statin use >3* per week
- smoking history non-smoker, ex-smoker, current smoker
- Aneurysm multiplicity record number of intra-dural aneurysms the patient has (treated or untreated)
- Family history number of 1 first degree and second degree relatives with UIA/SAH
- History of Autosomal Dominant Polycystic Kidney Disease yes, no
- Aneurysm location subclassification ICA paraclinoid (ophthalmic and superior hypophyseal) ICA (PCom), ICA other (anterior choroidal and bifurcation), ACA ACOM, ACA pericallosal, MCA, Posterior (basilar termination), Posterior (SCA), Posterior (AICA) Posterior (PICA)
- Bleb or irregularity of aneurysm recorded as present or absent from radiology report only. If not mentioned in report assumed to be absent. If no radiology report available, then recorded as NA.
- New/known diagnosis: patients in whom the aneurysm was known prior to the search period will be recorded as known diagnosis and otherwise as new diagnosis.

Data collection – aneurysm rupture/censoring events – local neurosciences units

At the time of baseline data collection locally available follow up will be recorded which will include:

• Date of last follow-up

- Date of death (if applicable)
- Cause of death (if applicable)
- Date of SAH (if applicable)
- Location of aneurysm causing SAH (if applicable)
- Date of aneurysm treatment (if applicable)
- Reason for aneurysm treatment (if applicable)

This data will be used for quality control of subsequent HES searches.

Data collection - aneurysm rupture/censoring events - central HES ONS data

Upon collection of all baseline data, a search of the Hospital Episode Statistics (HES) and Office for National Statistics (ONS) databases using the patient's NHS numbers be conducted. The use of a HES and ONS search is designed to maximise the identification of rupture events which are not treated in neurosurgical unit as subarachnoid haemorrhage. It will thus identify events managed in a district general hospital or those who die pre-hospital.

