This search will use ICD-10 codes as defined by the UK biobank Outcome Adjudication Group (Definitions of Stroke for UK Biobank Phase 1 Outcomes Adjudication Date: August 2017 Version: 1.1 https://biobank.ndph.ox.ac.uk/showcase/showcase/docs/alg_outcome_stroke.pdf). This will identify the following events:

- 1. Admission to hospital with aneurysmal subarachnoid haemorrhage (I60.0-I60.7)
- 2. Occlusive treatment of aneurysm.
- 3. Death diagnosed as subarachnoid haemorrhage in parts 1a-c of the death certificate.

All patients identified from the HES search with any of the above events will then have their medical notes re-evaluated by the local neurosurgery unit to confirm the HES report has accurately identified the event as aneurysm rupture or treatment.

A similar search will be repeated in Wales using NWIS/PEDW where NHS numbers are also used. Scotland does not use NHS numbers making searches more complex. However, a further search of equivalent database (SMR01) will be performed in Scotland using name and date of birth for identification.

Data collection - quality assurance - central HES ONS data

Additionally, all patients will be checked for possible SAH events that could have been miscoded.

Therefore, any patients with the codes:

- 1. Subarachnoid haemorrhage (other and unspecified) (I60.8-60.9)
- 2. Intracerebral haemorrhage (including intraventricular haemorrhage (I61.0-61.9)
- 3. Non-traumatic subdural haemorrhage (I62.00-I62.02)
- 4. Traumatic subarachnoid haemorrhage (S06.6X0, S06.6X9A, S06.6X9, S06.6X8A)

will have their casenotes reviewed for evidence the haemorrhage was aneurysmal.

Any patients with the following codes:

- 5. I46.1 sudden cardiac death
- 6. R96 other sudden death cause unknown
- 7. R98 unattended death

will have their casenotes reviewed to assess if their death was likely due rupture of their aneurysm.

Additionally, in at least one pilot site, all patients with the code

8. Cerebral infarction (63.0-63.9 & I64.X)

will have their casenotes reviewed to estimate rates of missed diagnosis for the whole cohort.

Where verification cannot be established from medical notes, any patients with codes in the specified possible miscoded SAH events will be assumed to be non-aneurysmal unless they have a procedure code indicating occlusive treatment of aneurysm within 30 days after the event, or they were coded as

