7.2 Sampling

7.2.1 Size of sample

Sample Size

There are no accepted methods for power calculation for validation studies of prognostic models. Therefore, usually the rule of thumb to have ten events for every covariate tested is applied.

For Aim 1, 6 covariates will be tested suggesting at least 60 SAHs will need to be captured. ISUIA recorded 51 ruptures in 1692 patients over 4.1 years. Sixty events may therefore be expected in 1,990 patients with 8,161 years of follow up.

For Aim 2, 120 events will need to be observed to account for the 6 additional commonly occurring covariates which would be expected in 3,981 patients with 16,332 years of follow up.

For autosomal dominant polycystic kidney disease (ADPKD) which has a low incidence, larger numbers of patients will be needed. Ten events in ADPKD are expected in 1360 patient years of follow up assuming the risk of SAH is not elevated and similar to the general population. However, 16,332 years follow up would only yield 195 years in patients with ADPKD (based on a population study which found 53/4436 IAs had ADPKD (Nurmonen 2017) and consistent with pilot data where 11/1025 cases examined to date had ADPKD). Therefore 113,905 years of follow up would be required to capture 10 ruptures amongst 1,340 years follow up in ADPKD patients. This would equate to 22,781 patients with 5 years of follow up (or applying the slightly looser rule of 5 events per prognostic factor this would require 56,952 years of follow up with 11,391 patients).

In a local pilot 1,415 cases were identified over 14 years in a population of 3 million with an anticipated 6,000 years of follow up. Extrapolating to England, Wales and Scotland 31,130 patients with 132,200 years follow up are available - well in excess of the target of 8,161 to validate PHASES in the general population, as well as the 16,332 to test the additional variables, but only just sufficient to answer the role of rarer predictors such as ADPKD. For reference PHASES was based on 29,166 years of patient follow up. Therefore, all cases that can be identified in England and Wales will be sought up to a maximum of 22,781.

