7.3 Recruitment

7.3.1 Sample identification

Patient identification

Due to most UIAs being detected during investigation for other conditions, HES coding for outpatient appointments cannot reliably identify patients with intracranial aneurysms and a local review suggested this may lead to a large underestimate of cases.

Therefore, patients will be identified by the direct clinical care teams at adult tertiary neurosurgical units in the UK treating patients with UIAs. All patients will be eligible whether seen in the centre, scanned in the centre or only discussed with the centre at MDT or on-call. Therefore, more than one search method may be applicable. Search methodology may be adapted to suit local case note and radiology records. We would recommend sequentially performing the following searches:

- 1. Electronic keyword searches of clinic letters, discharge summaries and MDTs. These capture most patients but risk missing patients not formally discussed with neurosurgery.
- 2. Electronic searches of cranial CTA, MRA and DSA reports for the term "aneurysm" excluding "no aneurysm". These searches capture all patients at the parent hospital but may miss regional patients scanned in district hospitals.
- 3. Searches of on call referrals may capture any further conservatively managed UIAs.

In some units, paper records of MDT or vascular clinics may be searched where electronic systems are not in place. Additionally, some units maintain prospective neurovascular databases which could be used for patient identification.

To reduce selection bias all participating centres will produce a written search strategy for their unit and perform a search over a locally prespecified time period. This period will be within the range of 1 January 2006 – 31 December 2020 (representing the implementation of PACS and the present), but may be shorter. The date of inclusion will be the date of the first document to identify the patient in that locally prespecified date range. Where aneurysms were diagnosed before the study dates, the aneurysm will be marked as "known diagnosis" and the date of inclusion remains that of the first document in the study date range.

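### Recruitment and GP censoring are UK-wide, but the named outcome searches cover only England, Wales and Scotland, and the study territory is given in four ways

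*Protocol*

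**What the plan says.** **Who is recruited.** Section 6: "The study will be conducted at up to 30 neurosurgery units in the UK". Section 7.3.1: "patients will be identified by the direct clinical care teams at adult tertiary neurosurgical units in the UK treating patients with UIAs". Section 1 describes the score as "whilst used by 24 out of 30 neurosurgery units in the UK", so a ceiling of 30 leaves no UK unit out. The eligibility criteria in Section 7.1 set no territory.

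**Where outcomes are looked for.** Section 5 names "a search of the Hospital Episode Statistics (HES) and Office for National Statistics (ONS) databases" by NHS number, then NWIS/PEDW for Wales, and then "a further search of equivalent database (SMR01) will be performed in Scotland using name and date of birth for identification". The data management text in Section 5 again lists HES, Wales and Scotland. Northern Ireland is not mentioned anywhere.

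**What coverage is claimed.** Section 3 plans to "link them to national databases for hospital admissions (HES/PEDW/SMR) for the UK". It goes on to say that a rupture will be captured wherever in the UK it happens.

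**When follow-up ends.** Section 5 takes the earliest of the HES search date, death, aneurysm treatment, or the date "the patient was unregistered with a GP in the UK". The migration correction under Aim 1 deals only with people who leave the UK.

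**Other statements of territory.** Section 2 sets the aim for Great Britain. Section 7.2.1 projects patient numbers for England, Wales and Scotland, and then says "all cases that can be identified in England and Wales will be sought".

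**The concern.** In a linked cohort, time at risk should be counted only where an event would be seen. Here the denominator follows the UK and the numerator follows three of its nations. Anyone living in the fourth nation keeps adding person-time up to the search date, with no central source for rupture, treatment or death. Unseen ruptures lower the numerator, and unseen deaths and treatments lengthen the denominator, so both errors push the estimated rupture risk down. Under Aim 1, Section 5 treats underestimation as the main threat and expects no significant overestimation. Aims 1 and 3 report absolute risks, which take this bias directly.

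The conflicting territory statements matter even if no Northern Ireland unit joins. Read literally, the recruitment sentence in Section 7.2.1 leaves out the Scottish patients for whom Section 5 plans a separate search.

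**Working it through.** **Step 1. Set the territories side by side.**

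| Element | Territory | Section |
|---|---|---|
| Aim | Great Britain | 2 |
| Participating units, patient identification | UK | 6, 7.3.1 |
| Projected numbers | England, Wales, Scotland | 7.2.1 |
| Cases to be sought | England and Wales | 7.2.1 |
| Named outcome searches | England, Wales, Scotland | 5 |
| Coverage claimed for those searches | UK | 3 |
| GP censoring, migration correction | UK | 5 |

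The plan needs separate Welsh and Scottish searches, so it does not itself treat HES as UK-wide. No row supplies outcomes for Northern Ireland, yet the recruitment and censoring rows include it.

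**Step 2. Reproduce the plan's sample size (Section 7.2.1).**

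- Annual rate r = 51 / (1,692 × 4.1) = 0.735%.
- Ten events in patients with ADPKD: 10 / r = 1,360 patient-years.
- Scaled to the cohort: 1,360 × 16,332 / 195 = 113,905 patient-years.
- Patients at 5 years each: 113,905 / 5 = 22,781, as stated.
- Expected ruptures: 113,905 × r = 837. Relative standard error of the pooled rate: 1 / √837 = 3.5%.

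**Step 3. Size of the bias.** Let f be the share of counted person-time with no outcome search, and assume the true rate is the same in covered and uncovered time. Then observed rate = r × (1 − f), and the relative understatement equals f. The documents do not give f, so the values below are assumptions. The 5-year risk is taken as 5 × the annual rate, which is 3.68% when f = 0.

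| Assumed f | Uncovered years (113,905 × f) | Ruptures unseen (837 × f) | 5-year risk read | Understatement in SE |
|---|---|---|---|---|
| 0.5% | 570 | 4 | 3.66% | 0.1 |
| 3.3% (one of 30 equal units) | 3,797 | 28 | 3.55% | about 1 |
| 5% | 5,695 | 42 | 3.49% | 1.4 |

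**Step 4. Allow for local notes.** If recruiting units find a share c of the otherwise unseen ruptures, the understatement is f × (1 − c). With f = 3.3% and c = 0.5 it is 1.7%.

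**Step 5. Shorter follow-up.** The pilot anticipated 6,000 / 1,415 = 4.24 years per patient. At the cap, 22,781 × 4.24 gives about 96,600 years and 710 ruptures. One thirtieth is about 24, and the relative standard error is 1 / √710 = 3.75%, so the bias is about 0.9 SE.

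**The case against.** **The territory may simply be loosely worded.** The protocol never says that a unit in Northern Ireland exists or will take part, and 30 is a ceiling. The aim in Section 2, the projection in Section 7.2.1 and the list of searches all point to Great Britain. This stands: the recruited-patient half of the concern is conditional. The territory contradictions and the GP rule for patients who move are not.

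**Local notes see ruptures too.** A reader might infer that no rupture in Northern Ireland could be seen at all. The documents do not support that. Section 5 has each unit record the date of SAH, death, treatment and last follow-up, and under Aim 1 it uses local SAH events to adjust the total risk. The help is partial, however. Local recording stops at baseline data collection. Section 3 says ruptures cannot be found from neurosciences records because many patients are admitted elsewhere. A pooled adjustment also does not restore individual event times for the C-index, Cox or Kaplan-Meier analyses.

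**A larger count is tempting.** One could take a thirtieth of the 132,200 years projected in Section 7.2.1 and get about 32 unseen ruptures. That projection is for England, Wales and Scotland only, so it holds no Northern Ireland time, and it exceeds the cap of 22,781 patients.

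**Scottish deaths.** A reader might also infer that deaths in Scotland go unrecorded, because the ONS search runs on NHS numbers and Scotland is matched by name and date of birth. Section 3 says the admission databases are linked to ONS for causes of death, and Section 5 plans similar searches in Scotland. The documents therefore do not show a gap. They leave the matching route for Scottish deaths unstated, which is a point to confirm.

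**The effect is small.** This also stands. Risks by individual PHASES score will have wider intervals than the pooled standard error used above.

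**Conclusion.** The inconsistency is real and should be corrected. Recruitment and GP censoring run UK-wide, the named outcome searches do not, and the UK-wide capture claimed in Section 3 is not delivered by the plan. Section 7.2.1 also disagrees with itself and with Section 5 about Scotland.

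The resulting bias is downward and small, and in relative terms at most the uncovered share of person-time. That share is not in the documents. Over an assumed 0.5% to 5% the 5-year risk would read 3.66% to 3.49% instead of 3.68%. The case of one of 30 equal units is roughly one standard error before local recovery, and less after it. These figures rest on the planning rate in Section 7.2.1, equal-sized units and equal rupture rates in covered and uncovered time. Patients who move to Northern Ireland cannot be counted from the documents. The sample size is unaffected.

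**What to change.** - State one territory in Sections 2, 3, 6, 7.2.1 and 7.3.1, equal to the nations whose admissions and deaths are both searched, and limit participating units to it.
- Correct the Section 3 statements of UK-wide capture to match.
- In Section 5, censor when GP registration in those nations ends, rather than registration in the UK.
- In Section 7.2.1, bring the England and Wales recruitment sentence into line with the Scottish search in Section 5.
- Confirm that the ONS death linkage described in Section 3 applies to Scottish patients, and state how they are matched to it without an NHS number.

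If a Northern Ireland unit is wanted, the alternative is to add an admissions and deaths search there and keep the UK as the territory. That costs a further data application.

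The main route is mostly a change of wording, cheapest to make before the linkage applications are settled. Its price is the loss of any Northern Ireland unit's patients and slightly shorter follow-up for those who move out of the covered nations.
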